#### 10.3.4.1.2 Primary Safety Analysis

The primary safety analysis will be done using the PP population.

The analysis of the primary safety endpoint will entail a one-sided test of non-inferiority using the Farrington-Manning method with a non-inferiority bound of 15%. If we denote  $s_{pr}$  to be the safety event rate in the *ProSpace Group* and  $s_c$  to be the safety event rate in the *Control Group*, the primary safety hypothesis is as follows:

$$H_0: s_{pr} - s_c \ge 0.15$$
 vs  $H_1: s_{pr} - s_c < 0.15$ 

The study will be a success if the test is significant against a one-sided p-value cut-off of 0.025.

The SAS code for analyzing the primary safety endpoint is as follows:

```
PROC FREQ ;
TABLES TRTPN*GRADE1 / RISKDIFF (NONINF MARGIN=0.15 METHOD=FM) ;
RUN ;
```

Statistical Analysis Dlan	Client/Project	BioProtect BP-007
Statistical Allalysis Flan	Version and Date	V2 05-DEC-2021

where TRTPN is the treatment group and GRADE1 is a binary variable indicating whether a subject experienced a primary safety event (1 = event, 0 = no event).

### 10.3.4.1.3 Sensitivity Analysis for Primary Safety Endpoint

The analysis of the primary safety endpoint will be repeated as a sensitivity analysis using the period from marking through Day 197 (6 months plus 14 days).

To evaluate the potential impact of missing data on the primary safety endpoint, the following sensitivity analyses will be performed using the ITT population: A tipping point analysis will be performed by imputing the range of possible combinations of successes and failures for the missing subject values in both groups, ranging from all failures to all successes. For every imputation combination across the two groups, the effect on the primary safety hypothesis will be reported to evaluate the robustness of the analysis to patterns of missing data across the two groups. The tipping point analysis will be performed using the ITT population.

In addition, to evaluate the robustness of the safety outcome, Kaplan-Meier estimates of time to Primary Safety AE will be provided. Based on the Kaplan-Meier curves, estimates for the proportion of subjects experiencing AEs of interest, along with the 95% confidence interval for the difference between the groups, will be provided at 183 days (6 months) from the marking date.

## 10.3.4.1.4 Poolability Analysis for Primary Safety Endpoint

Poolability analysis will be done using the PP population.

The Poolability will be examined at two levels:

- 1. Location of site based on US versus outside US (OUS)
- 2. Across individual sites regardless of location

Descriptive statistics of the co-primary safety endpoint will be presented by location (US and OUS) and by site. To test the poolability across US and out of US safety data, a logistic model will be used. In this model the dependent variable is occurrence of AE, and independent variables will include treatment group, location (US, OUS), and group-by-location interaction as fixed factors. The term of interest is the potential interaction between the group and location. If the p-value for the interaction is greater than 0.15, then the data will be considered suitable for pooling at the US-OUS location level. If the p-value is less than 0.15 then additional analyses of the impact of the location will be considered, and the corresponding estimate of the difference will be provided.

In this study some sites are expected to enroll a small number of subjects. Having several small sites might prevent the convergence of logistic regression. Should that occur the smallest sites within geographic location will be pooled together until the model converges.

## 10.3.4.1.5 Subgroup Analyses for Primary Safety Endpoint

The impact of different covariates on the primary safety outcome will be evaluated. The following covariates will be examined:

- Age, divided into two age groups of less than 65 years and greater than or equal to 65.
- Race

If any baseline factor is found to be significantly different between the treatment groups, it will also be tested as a covariate.

Covariate analyses for the primary safety endpoint will be done using logistic regression. Testing will focus on the covariate by treatment interaction to assess whether safety is dependent on covariate levels. In addition, descriptive statistics by covariate level will be presented.

Statistical Analysis Dlan	Client/Project	BioProtect BP-007
Stausucai Analysis Plan	Version and Date	V2 05-DEC-2021

Each covariate will be evaluated separately.

### 10.3.4.2 Co-Primary Efficacy Endpoint and Analysis

### **10.3.4.2.1 Primary Efficacy Endpoint**

The primary efficacy endpoint is a binary assessment of whether a subject obtains at least a 25% reduction at 21 days post-implantation in the volume of the rectum receiving greater than or equal to 70 Gy ( $V_{Rectum}$  70). The primary efficacy endpoint will be assessed only for subjects who are randomized to the *ProSpace Group* and receive the ProSpace device.

### 10.3.4.2.2 Primary Efficacy Analysis

The primary efficacy analysis will be done using the PP population.

The primary effectiveness analysis will be completed using a one-sided 0.025 exact binomial test. If we denote  $v_e$  to be the percentage of subjects meeting the  $V_{Rectum}$  70 success criteria in the *ProSpace Group*, the primary hypothesis is as follows:

$$H_0: v_e \le 75.0\%$$
 vs  $H_1: v_e > 75.0\%$ 

The exact binomial 95% CI for the success rate will also be provided. The SAS code for analyzing the primary efficacy endpoint for the *ProSpace Group* subjects is as follows:

```
PROC FREQ ;
TABLES V70 / BINOMIAL (P=0.75) ;
EXACT BINOMIAL ;
RUN ;
```

where V70 is a binary variable indicating whether a subject achieved at least a 25% reduction in  $V_{\text{Rectum}}$ 70 (1 = response, 0 = no response).

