2.2.2.2 PRIMARY EFFECTIVENESS ENDPOINT

The primary effectiveness endpoint will be evaluated in subjects with prostate cancer who are undergoing radiotherapy by means of IMRT and who receive the balloon, with individual patient success defined as a reduction of at least 25% of the volume of the rectum receiving greater or equal to 70 Gy (V_{Rectum} 70) when compared to pre-implantation values. The study will be considered a success if the rate is significantly greater than 75%; the hypothesis will be evaluated using a one-sided exact binomial test as detailed in **Section 2.3**.

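### The SAS code for the co-primary efficacy test names no response level and, under the PROC FREQ default, tests non-response instead of the success rate against 75%

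*SAP*

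**What the plan says.** SAP section 10.3.4.2.2 defines v_e as the percentage of balloon subjects who meet the V70 success criterion. The null is v_e at or below 75% and the alternative is v_e above 75%. On the test it says: "The primary effectiveness analysis will be completed using a one-sided 0.025 exact binomial test". On estimation it says: "The exact binomial 95% CI for the success rate will also be provided". Protocol section 2.2.2.2 agrees: "The study will be considered a success if the rate is significantly greater than 75"%, and protocol section 2.3.4.3 gives the same hypotheses, test and one-sided 0.025 level.

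The same SAP section then gives the code for this analysis. It is a PROC FREQ step with "TABLES V70 / BINOMIAL (P=0.75") and an EXACT BINOMIAL statement. V70 is coded "1 = response, 0 = no response". The code has no `LEVEL=` option, no `ORDER=` option and no format, and no other section says which level is analysed. SAP section 10.1 fixes the software as SAS 9.4.

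**The concern.** A one-sample binomial procedure has to know which of the two levels is the event. When the code does not say, the software's default decides. For a variable coded 0/1 with no reordering, the first level is 0, which here means no response. The code would then set the failure rate against 75%, although the hypothesis concerns the success rate.

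Two outputs would be wrong if the code were run as printed: the one-sided p-value for a co-primary endpoint, and the exact confidence interval, which would describe failures and not the promised success rate. A device that works tends to have a failure rate far below 75%, so the printed p-value would be extremely small whether or not the success rate exceeded 75%. The p-value alone would give no warning. The mismatch would most likely surface only once data were in hand, when the sponsor would have to depart from its own printed code for a pivotal endpoint.

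**Working it through.** **Inputs.** Null rate 0.75, one-sided alpha 0.025, exact binomial (SAP 10.3.4.2.2). Evaluable balloon subjects n = 136 and assumed true rate 87.5% (SAP section 6; protocol 2.3.4.4.1). V70 = 1 for response, 0 for no response (SAP 10.3.4.2.2).

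**Assumptions about SAS, which was not run.** (a) With no level named, PROC FREQ analyses the first sorted level, V70 = 0. (b) It prints the one-sided p for the upper tail if the estimate exceeds the null value, and otherwise for the lower tail.

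**Step 1: reproduce the plan's figure.** Let X be the number of responders. The cutoff is the smallest x with P(X ≥ x | 136, 0.75) ≤ 0.025.

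- P(X ≥ 112) = 0.0267, too large.
- P(X ≥ 113) = 0.0159, so the cutoff is 113 (113/136 = 83.1%) and the exact size is 0.016.
- Power at 87.5%: P(X ≥ 113 | 136, 0.875) = 0.949, against the stated 95%.

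The sample size was therefore computed for the test in the text.

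**Step 2: evaluate the code as printed.** Let Y = 136 − X be the number of non-responders, compared with 0.75.

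- Estimate at or below 0.75: the lower tail is printed. P(Y ≤ 91) = 0.021 and P(Y ≤ 92) = 0.032, so p ≤ 0.025 when Y ≤ 91, that is X ≥ 136 − 91 = 45 (33.1%).
- Estimate above 0.75: the upper tail is printed. P(Y ≥ 113) = 0.0159, so p ≤ 0.025 when Y ≥ 113, that is X ≤ 136 − 113 = 23 (16.9%).

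**Step 3: compare over all 137 possible results.** The two disagree at 0–23 responders (24 results) and 45–112 responders (68 results): 24 + 68 = 92. In every one of these the code is significant and the stated test is not.

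| Responders | Stated one-sided p | Printed one-sided p | Printed estimate |
|---|---|---|---|
| 102/136 (75.0%) | 0.55 | 3e-34 | 34/136 = 25.0% (95% CI 18.0% to 33.1%) |
| 112/136 (82.4%) | 0.027 | 1e-44 | 24/136 = 17.6% |
| 119/136 (87.5%) | 0.00025 | 3e-53 | 17/136 = 12.5% (95% CI 7.5% to 19.3%) |

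At 119/136 the interval the SAP promises, for the success rate, is 80.7% to 92.5%.

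Counting results gives them equal weight, so probabilities are more informative. At a true success rate of 75% the lower-tail p printed by the code is at or below 0.025 with probability essentially 1, against 0.016 for the stated test. At a true rate of 40% the probability is still 0.96.

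**Step 4: other sample sizes.** With n = 125 the stated cutoff is 104, and the code is significant at 42 or more, or 21 or fewer. With n = 148 (the planned balloon enrolment) the stated cutoff is 122, and the code is significant at 49 or more, or 26 or fewer.

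**Step 5: the safety code, as a side check.** SAP section 10.3.4.1.2 describes its variables as follows: "where TRTPN is the treatment group and GRADE1 is a binary variable"; the order of the treatment levels is not given. Assuming the default takes the first column (GRADE1 = 0) and subtracts the second row from the first, the difference is (1 − s_pr) − (1 − s_c) = s_c − s_pr when ProSpace is first. Non-inferiority then means s_c − s_pr > −0.15, which is the stated s_pr − s_c < 0.15. For 26/136 against 14/68 both routes give p = 0.0013. If Control were first, the comparison would be reversed: 48/136 against 14/68 would give about 0.00001, where the stated test gives 0.48. This part is conditional. It shows an unstated ordering, not an error.

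**The case against.** The strongest reply is that the text governs. Protocol and SAP repeatedly state the success rate, the direction and the test, so no reader could think non-response was the target. The code is also a fragment: it has no dataset name and no population filter, and a format or sort order could sit in the full program. Anyone running it would see an estimate such as 12.5% where a success rate above 75% was expected. Finally, the default behaviour comes from knowledge of SAS and not from the documents.

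Much of this stands. The planned type I error, power and hypothesis are sound, and the wrong level would probably be noticed. The count of 92 results includes implausible ones. The default is an assumption: if an unstated format put response first, the level would be right. The tail point is also small, because with response selected the lower tail is significant only at 91 or fewer responders (66.9%), which nobody could read as success.

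It does not remove the conflict. The SAP presents this code as the code for the endpoint, does not call it illustrative, and does not say that text overrides code. Even on the most generous reading, the code leaves unstated the level that the hypothesis requires.

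**Conclusion.** The concern holds, as something that should be fixed before the analysis. On the assumed SAS default, the printed code tests and estimates the non-response rate, so its one-sided p-value cannot be used to judge whether the success rate exceeds 75%. At n = 136 it would be significant from 45 responders upward, where the stated test requires 113. The fault is confined to the code: hypotheses, alpha, sample size and power are unaffected. At the planned success rate both versions are significant, but the confidence interval would still be the wrong one. If a format or ordering that the SAP does not mention puts response first and the upper tail is read, there is no disagreement. The safety code needs only a clarification.

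**What to change.** In SAP section 10.3.4.2.2, change the statement to `TABLES V70 / BINOMIAL(LEVEL='1' P=0.75)` and keep the EXACT BINOMIAL statement. Add a sentence that success requires the upper-tail exact probability P(X ≥ x), computed under a 75% success rate, to be at most 0.025. In section 10.3.4.1.2, add a sentence that ProSpace is the first level of TRTPN, so that the default column tests s_pr − s_c < 0.15. Running both pieces of code on a small dummy dataset would confirm the levels and the tail.

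The cost is one code option and two sentences. Hypotheses, alpha, sample size and data collection do not change.

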#### 10.3.4.2.3 Sensitivity Analysis for Primary Efficacy Endpoint

To evaluate the potential impact of missing data on the primary efficacy endpoint, a tipping point analysis will be performed that considers all possible imputations of the missing data. The analysis will be based on the ITT population.

#### 10.3.4.2.4 Poolability Analysis for Primary Efficacy Endpoint

Poolability analysis will be done using the ProSpace PP population.

The Poolability will be examined at two levels:

- 1. Location of site based on US versus outside US (OUS)
- 2. Across sites regardless of location (US or OUS)

Descriptive statistics of the co-primary efficacy endpoint will be presented by location (US, OUS) and by site. To test formally poolability across US and out of US safety data, a logistic model will be used. In this model the dependent variable is the primary efficacy endpoint, and independent variable will be location (US, out of US) as a fixed factor, with baseline  $V_{Rectum}$  70 as a covariate. If the p-value for the location variable is greater than 0.15, then the data will be considered suitable for pooling at the US-OUS location level. If the p-value is less than 0.15 then additional analyses of the impact of the location will be considered, and the corresponding estimate of the difference will be provided.

In this study some sites are expected to enroll a small number of subjects. Having several small sites might prevent the convergence of logistic regression. Should that occur the smallest sites within geographic location will be pooled together until the model converges.

Statistical Analysis Dlan	Client/Project	BioProtect BP-007
Stausucal Analysis Flan	Version and Date	V2 05-DEC-2021

## **10.3.4.2.5 Subgroup Analyses for Primary Efficacy Endpoint**

The impact of different covariates on the primary safety outcome will be evaluated. The following covariates will be examined:

- Age, divided into two age groups of less than 65 years and greater than or equal to 65.
- Race

If the primary efficacy endpoint is found to be significantly dependent on any baseline factor, that factor will also be tested as a covariate.

Covariate analyses for the primary safety endpoint will be done using a logistic regression. Testing will focus on the covariate by treatment interaction to assess whether safety is dependent on covariate levels. In addition, descriptive statistics by covariate level will be presented.

Each covariate will be evaluated separately.

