2.3.4.3 PRIMARY EFFICACY ANALYSES

The primary effectiveness endpoint is assessed only for subjects who receive the balloon device. The primary effectiveness endpoint is a binary assessment of whether a subject obtains at least a 25% reduction in the volume of the rectum receiving greater than or equal to 70 Gy (V_{Rectum} 70). If we denote v_e to be the percentage of subjects meeting the V_{Rectum} 70 success criteria in the balloon arm, the primary hypothesis is as follows:

H₀:
$$v_e \le 75.0\%$$
 vs H₁: $v_e > 75.0\%$

This analysis will be completed using a one-sided 0.025 exact binomial test with subjects who participate in the primary safety endpoint analysis. The exact 95% CI for the success rate will be provided as well.

Sensitivity analyses will include a tipping point analysis. To assess the validity of pooling the results across the study sites, a Likelihood Ratio chi-square test will be used to assess the homogeneity across the study sites. A p-value of greater than 0.15 will be considered supportive of pooling of the study sites.

Results will also be summarized by age greater than or equal to 65 years versus less than 65 years, and race. A likelihood ratio chi-square test will be used to evaluate the null hypothesis the factors are not associated with outcome.

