# **10** Statistical Methods

## **10.1 General Statistical Considerations**

Study data will be made available in listings or electronic files, and study data will be listed by subject with the randomized treatment indicated. The study results will be summarized using descriptive statistics by randomized treatment. Summaries of baseline information will also include a total column. Standard numeric descriptive statistics include the n (observed values), mean (including the 95% confidence interval), standard deviation, median, minimum, and maximum values. Categorical data will be summarized with counts and percentages calculated based on non-missing values. Measures summarized across multiple visits will be summarized by visit, and a change from baseline will be provided for numeric variables.

A two-sided p-value of less than or equal to 0.05 or a one-sided p-value of less than or equal to 0.025 will be considered statistically significant unless otherwise specified.

All statistical analyses and summaries will be generated using SAS version 9.4.

<sup>1 HHS, FDA (1998). Guidance for industry: E9 Statistical Principles for Clinical Trials

<sup>2 SAS software. Version 9.4. Copyright © 2016 SAS Institute Inc., Cary, NC, USA.

Statistical Analysis Dlan	Client/Project	BioProtect BP-007
Statistical Allalysis Flan	Version and Date	V2 05-DEC-2021

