#### 10.3.2 Demographics and Baseline Characteristics

Demographic and baseline information will be summarized for the PP population using descriptive statistics. Categorical variables (gender, race, clinical stage at baseline) will be summarized using frequency and percentages. Numeric variables (age, height, weight, BMI, AUA Symptom Score at baseline) will be summarized using descriptive statistics as total number of subjects surveyed (N), mean, median, standard deviation, minimum, maximum, and inter-quartile range.

The homogeneity of the baseline characteristics of the two randomized groups will be evaluated using Fisher's Exact Test, Likelihood Ratio chi-square tests, or Rank-Sum tests.

Medical history will be listed and will include descriptions of prior conditions and treatments, especially if related to the prostate, bladder, rectum, anus, or perineal area; and current medications and other drug

Statistical Analysis Dlan	Client/Project	BioProtect BP-007
Statistical Analysis Plan	Version and Date	V2 05-DEC-2021

therapies indicated for treatment of prostate cancer. The overall number and percentage of subjects with one or more medical history findings by type will be summarized.

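### The efficacy subgroup section admits extra covariates because the efficacy outcome already depends on them in the same data, then tests them on that same association

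*SAP*

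**What the plan says.** Protocol section 2.3.4.3 plans two efficacy subgroup factors: "Results will also be summarized by age greater than or equal to 65 years versus less than 65 years, and race". It tests each for association with outcome by a likelihood ratio chi-square test.

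SAP section 10.3.4.2.5 repeats age and race and then adds: "If the primary efficacy endpoint is found to be significantly dependent on any baseline factor, that factor will also be tested as a covariate". It continues: "Testing will focus on the covariate by treatment interaction to assess whether safety is dependent on covariate levels", and ends: "Each covariate will be evaluated separately". It gives no closed list of factors, names no screening test, and sets no significance level, adjustment or exploratory label for these tests. The general rule in SAP section 10.1 therefore applies: "A two-sided p-value of less than or equal to 0.05 or a one-sided p-value of less than or equal to 0.025". The 0.0167 Bonferroni level in SAP section 10.2 covers the labelling analyses only. SAP section 3.2, which lists changes to the planned analyses, does not mention the added rule.

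Protocol section 2.3.4.3 and SAP section 10.3.4.2.1 both restrict the efficacy endpoint to subjects who received the balloon. Table 14.2.1.3 in SAP section 12 is a covariate analysis of the reduction in V_Rectum 70 in the ProSpace per-protocol population.

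**The concern.** A subgroup section should show whether the efficacy result holds across kinds of patient, using factors chosen without sight of the outcome. Here a factor beyond age and race enters because V_Rectum 70 success already varies with it in the trial data. It is then tested against that same outcome in the same subjects. The second result looks like confirmation but carries no new information.

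Because the rule covers any baseline factor, the number of looks is not bounded. At stake is a statement in a pivotal device report that V_Rectum 70 success depends on some factor, when the pattern may be chance picked from several candidates. At the planned response rate there would be few non-responders, so such patterns are easy to find.

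**Working it through.** **The plan's own figure.** The documents give no error rate for the covariate tests. The nearest stated figure is the efficacy power in protocol section 2.3.4.4.1: at least 95% with 136 evaluable balloon subjects, a true rate of 87.5% against 75%, and a one-sided exact binomial test at 0.025. Recomputed, success needs at least 113 of 136. The exact type I error is 0.0159 and the power is 0.949, which agrees to rounding. At 87.5% success the expected number of non-responders is 136 × 0.125 = 17.

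**Why selection and test coincide.** The endpoint exists in one arm, so a covariate-by-treatment term cannot be estimated for it. What remains is the association between factor and success, which is the dependence named in the selection rule. If the same test is used for both steps, a selected factor passes the second step with certainty. If the two steps use slightly different tests (say, a rank-sum test and then logistic regression), it passes almost always.

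**How many factors.** This has to be assumed. SAP section 10.3.2 lists gender, race and clinical stage, and age, height, weight, BMI and AUA score. Gender is constant because all subjects are male (SAP section 8). Age and race are prespecified. That leaves five possible extras: clinical stage, height, weight, BMI and AUA score. Baseline V_Rectum 70, a covariate in the poolability model of SAP section 10.3.4.2.4, makes six.

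**Chance of at least one spurious added factor.** With k independent factors, none related to outcome, each read at 0.05, the chance is 1 − 0.95^k.

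| Factors | k | 1 − 0.95^k |
|---|---|---|
| Age and race only (protocol) | 2 | 0.098 |
| Age, race, baseline V_Rectum 70 | 3 | 0.143 |
| Listed extras | 5 | 0.226 |
| Extras plus baseline V_Rectum 70 | 6 | 0.265 |
| All eight, including age and race | 8 | 0.337 |

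**Check by simulation** (136 subjects, 87.5% success, no true dependence, assumed covariate distributions):
- Five extras, with one logistic likelihood ratio test per factor and height, weight and BMI correlated (3,000 trials): 0.204.
- Six extras, with likelihood ratio chi-square for clinical stage and rank-sum for the numeric factors (4,000 trials): 0.252.

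Together these give about 20% to 27%. Correlation lowers the figure. For eight factors with equally correlated test statistics the rate falls from 0.336 at correlation 0 to 0.251 at 0.5 and 0.157 at 0.8. The floor is 0.05, reached if the factors were perfectly correlated. A longer list raises it: ten independent factors give 0.401.

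**The case against.** The strongest reply is that, read literally, SAP section 10.3.4.2.5 is not circular. It speaks of the safety outcome and a treatment interaction, so selection would be on efficacy and testing on safety. That wording appears to be carried over from the safety section, and it cannot be what is meant: Table 14.2.1.3 analyses V_Rectum 70 reduction in the balloon group alone. The selection sentence itself is specific to efficacy. Correcting the outcome name would leave it in place.

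It can also be said that the sentence is conditional and does not order a screen of every factor; that retesting adds no false positives beyond those from screening; and that a false signal here suggests heterogeneity, which does not favour the sponsor. All three are fair. The first means that the factor count is an assumption. The second means that the inflation comes from the number of looks, while the retest adds only the appearance of confirmation. The protocol's own age and race tests are also unadjusted, so lack of adjustment alone is not the complaint.

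A reader might infer that about one trial in three would report a spurious factor because of this rule. The documents do not support that. The figure needs eight independent factors, a count that the documents do not give, and it includes age and race, which the protocol prespecifies.

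A reader might also extend the point to SAP section 10.3.4.1.5, which says: "If any baseline factor is found to be significantly different between the treatment groups, it will also be tested as a covariate". That rule selects on imbalance between arms, not on outcome, so it is not circular. With five factors beyond age and race it would add at least one by chance in 1 − 0.95^5 = 0.226 of trials, but that is not a false-positive rate. A spurious interaction needs both a chance imbalance and a chance interaction: about 5 × 0.05 × 0.05 = 0.0125 if these are independent. Removing a check on imbalanced factors for so small a gain is a debatable trade, and it is not proposed here.

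**Conclusion.** The point holds for the outcome-driven sentence in SAP section 10.3.4.2.5. A factor admitted by it is tested on the association that admitted it, and the resulting p-value should not be read as evidence. The chance of at least one spurious added factor is about 20% to 27%. This rests on five or six assumed extra factors, a 0.05 level taken from the SAP's general rule, and little or moderate correlation among the factors.

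The consequence is confined to subgroup reporting. No covariate result enters the exact binomial efficacy test, the Farrington-Manning safety test or the labelling tests at 0.0167. The change is still worth making, because it is specific and nearly free, and the section needs correcting anyway: its stated interaction test cannot be run on a one-arm endpoint.

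**What to change.** In SAP section 10.3.4.2.5:

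- Delete the sentence that admits factors on which the efficacy endpoint is found to depend.
- Use a list closed before database lock: age (under 65 versus 65 or over), race, and baseline V_Rectum 70.
- Replace the safety-outcome and treatment-interaction wording with a single-arm association test: likelihood ratio chi-square for age and race, as in protocol section 2.3.4.3, and logistic regression for baseline V_Rectum 70 kept continuous.
- Report success rates with exact 95% confidence intervals by level of age and race.
- Label the results exploratory. This is needed even with a closed list, since three independent null tests still give a 14% chance of at least one p-value at or below 0.05.

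Leave the baseline-imbalance sentence in SAP section 10.3.4.1.5 as it stands.

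The cost is a short SAP edit, with no new data, subjects or procedures. The downside is that an unexpected factor can be reported only as a post hoc observation.
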